<sup>x Potential for very low sensitivity leading to misclassification. This variable will be reported if feasible.

Variable	Role	Operational definition
History of hypertension	Outcome: CV risk factor	Defined as $\geq 1$ ICD-10 diagnosis code for hypertension or $\geq 1$ prescription dispensing (as identified by ATC code[s]) for an antihypertensive in the 12 months prior to or on the day of the index tofacitinib dispensing.
		Complete list in ANNEX 8. LIST OF ATC CODES FOR ANTIHYPERTENSIVES.
History of hyperlipidaemia	Outcome: CV risk factor	Defined as $\geq 1$ ICD-10 diagnosis code for hyperlipidaemia or $\geq 1$ prescription dispensing (as identified by ATC code[s]) for a statin or other antihyperlipidaemic in the 12 months prior to or on the day of the index tofacitinib dispensing.
		Complete list in ANNEX 9. LIST OF ATC CODES FOR ANTIHYPERLIPIDAEMICS.
History of coronary artery disease (defined as MI, stroke, CABG [coronary artery bypass graft], or PCI [percutaneous coronary intervention])	Outcome: CV risk factor	Defined as $\geq 1$ ICD-10 diagnosis code for MI or stroke or $\geq 1$ procedure code for CABG or PCI in the 12 months prior to or on the day of the index tofacitinib dispensing.
History of chronic kidney disease	Outcome: CV risk factor	Defined as $\geq 1$ ICD-10 diagnosis code for chronic kidney disease in the 12 months prior to or on the day of the index tofacitinib dispensing.
History of stable angina pectoris	Outcome: CV risk factor	Defined as ≥1 ICD-10 diagnosis code for stable angina pectoris in the 12 months prior to or on the day of the index tofacitinib dispensing.
Initiating tofacitinib with $\geq 1$ CV risk factor	Outcome: CV risk factor	Defined as ≥1 CV risk factor (as listed and defined above) identified in the 12 months prior to or on the day of the index tofacitinib dispensing.

 Table 3.
 Operational definitions of study variables in the selected databases

Variable	Role	Operational definition

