Initiating tofacitinib with ≥1 CV risk factor and no prior use of an alternative therapy (i.e., biologic)	Outcome: CV risk factor	
 
Defined as ≥1 CV risk factor (as listed and defined above) identified in the 12 months prior to or on the day of the index tofacitinib dispensing—AND—0 prescription medication dispensings for a biologic (as identified by ATC code) in the 12 months prior to and including the date of the index tofacitinib prescription dispensing.
 
Complete list of biologics in ANNEX 6. LIST OF ATC CODES FOR MEDICATIONS OF INTEREST TO AVOID WHILE TAKING TOFACITINIB.
 

 Table 3.
 Operational definitions of study variables in the selected databases

Assessment of CV risk factors while receiving tofacitinib therapy (duration of tofacitinib therapy defined in Section 9.3.3) (will be stratified by sex as outlined in Section 9.7.1.2.2.1.3 [Patients with CV risk factors])

Elderly (patients 65 years and older)	Outcome: CV risk factor	Defined as patients aged 65 years or older while receiving tofacitinib.
Current smoker x	Outcome: CV risk factor	Defined as $\geq 1$ ICD-10 diagnosis code for tobacco use disorder or $\geq 1$ procedure code for counselling visits for smoking or $\geq 1$ prescription dispensing (as identified by ATC code[s]) for a nicotine replacement product while receiving tofacitinib.
Diabetes	Outcome: CV risk factor	Defined as ≥1 ICD-10 diagnosis code for diabetes while receiving tofacitinib therapy.
Hypertension	Outcome: CV risk factor	Defined as ≥1 ICD-10 diagnosis code for hypertension or ≥1 prescription dispensing (as identified by ATC code[s]) for an antihypertensive while receiving tofacitinib. Complete list in ANNEX 8. LIST OF ATC CODES FOR
		ANTIHYPERTENSIVES.
Hyperlipidaemia	Outcome: CV risk factor	Defined as $\geq 1$ ICD-10 diagnosis code for hyperlipidaemia or $\geq 1$ prescription dispensing (as identified by ATC code[s]) for a statin or other antihyperlipidaemic while receiving tofacitinib.
		Complete list in ANNEX 9. LIST OF ATC CODES FOR ANTIHYPERLIPIDAEMICS.

Variable	Role	Operational definition
Coronary artery disease (defined as MI, stroke, CABG [coronary artery bypass graft], or PCI [percutaneous coronary intervention])	Outcome: CV risk factor	Defined as ≥1 ICD-10 diagnosis code for MI or stroke or ≥1 procedure code for CABG or PCI while receiving tofacitinib therapy.

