### 9.7.1.3.3. Use in patients with CV risk factors

The proportion of patients with one or more CV risk factors, identified prior to tofacitinib initiation, will be described and tabulated overall and for each individual CV risk factor (i.e., elderly, current or past smokerx, history of diabetes, history of hypertension, history of hyperlipidaemia, history of coronary artery disease, history of chronic kidney disease, history of stable angina pectoris) for CV and Malignancy Reporting Period 1, CV and Malignancy

Reporting Period 2, and CV and Malignancy Reporting Period 3.ww Proportions will be stratified by approved indication and sex.

The proportion of patients with one or more CV risk factors, identified prior to tofacitinib initiation and no prior use of an alternative therapy (i.e., biologic), will be described and tabulated overall and for each individual CV risk factor (i.e., elderly, current or past smokerx, history of diabetes, history of hypertension, history of hyperlipidaemia, history of coronary artery disease, history of chronic kidney disease, history of stable angina pectoris) for CV and Malignancy Reporting Period 1, CV and Malignancy Reporting Period 2, and CV and Malignancy Reporting Period 3.ww Proportions will be stratified by approved indication and sex.

The proportion of patients who discontinue tofacitinib after developing one or more CV risk factors while taking tofacitinib will be described and tabulated overall and for each individual CV risk factor (i.e., elderly, current smokerx, diabetes, hypertension, hyperlipidaemia, coronary artery disease, chronic kidney disease, stable angina pectoris) for CV and Malignancy Reporting Period 1, CV and Malignancy Reporting Period 2, and CV and Malignancy Reporting Period 3.ww Proportions will be stratified by approved indication and sex.

The proportion of patients who continue tofacitinib after developing one or more CV risk factors while taking tofacitinib will be described and tabulated overall and for each individual CV risk factor (i.e., elderly, current smokerx, diabetes, hypertension, hyperlipidaemia, coronary artery disease, chronic kidney disease, stable angina pectoris) for CV and Malignancy Reporting Period 1, CV and Malignancy Reporting Period 2, and CV and Malignancy Reporting Period 3.ww Proportions will be stratified by approved indication and sex.

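### The coronary artery disease row in Table 3 counts stroke and omits coronary diagnoses other than MI, so its separately reported figure cannot be read under its label

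*Protocol*

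**What the plan says.** Protocol section 9.3.2, Table 3, lists among the CV risk factors before initiation "History of coronary artery disease (defined as MI, stroke, CABG [coronary artery bypass graft], or PCI [percutaneous coronary intervention". The operational definition asks for at least one "ICD-10 diagnosis code for MI or stroke or" at least one "procedure code for CABG or PCI in the 12 months prior to or on the day of the index tofacitinib dispensing".

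The on-treatment block carries the same variable, "Coronary artery disease (defined as MI, stroke, CABG [coronary artery bypass graft], or PCI [percutaneous coronary intervention", with the definition "Defined as ≥1 ICD-10 diagnosis code for MI or stroke or ≥1 procedure code for CABG or PCI while receiving tofacitinib therapy".

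A separate row, "History of stable angina pectoris", covers stable angina and has an on-treatment counterpart. The hyperlipidaemia row can be met by a dispensing "for a statin or other antihyperlipidaemic in the 12 months prior to or on the day of the index tofacitinib dispensing".

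Section 9.7.1.2.2.1.3 reports each CV risk factor individually as well as in the composite, stratified by indication and sex, and also crosses the baseline factors with no prior biologic. Section 9.7.1.3.3 repeats this by CV and Malignancy Reporting Period, where the row appears under the short label in "history of coronary artery disease, history of chronic kidney disease".

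Section 9.3.2 calls the algorithms and codes preliminary and leaves their refinement to the SAP.

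**The concern.** The label and the content differ in both directions. Stroke is a cerebrovascular event, yet it makes the row positive. Chronic ischaemic heart disease and unstable angina are coronary diagnoses, yet neither makes it positive unless an MI, stroke, CABG or PCI is also coded.

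The row is one of the individually tabulated figures under Primary Objective 2 and Secondary Objective 2. Section 7 says the 2021 signal procedure identified MI as an important risk and restricted use in patients with CV risk factors. A reader who wants to know how often tofacitinib was started in coronary patients before and after the 2021 materials would turn to this row, and it would not answer the question. A change between periods could come from stroke patients, from coronary events, or from both.

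**Working it through.** The protocol states no figure that could be reproduced here, so the check is a textual one.

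**Step 1: apply the definition as written.**

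| Coded in the 12 months up to index | Coronary artery disease row | Stable angina row |
|---|---|---|
| MI, CABG or PCI | yes | no |
| Stroke only, no coronary disease | yes | no |
| Chronic ischaemic heart disease or unstable angina only | no | no |
| Stable angina only | no | yes |
| Old-MI code only | depends on the SAP code list | no |

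The second and third lines are the defect. The fifth is open because the definition asks for a diagnosis code for MI and does not limit it to acute MI. The protocol restricts MI to recent events only in the VTE block, where the window is 3 months.

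**Step 2: compare with the neighbouring rows.** The baseline CV rows for diabetes, hypertension, hyperlipidaemia, chronic kidney disease and stable angina each accept at least one diagnosis code for the condition they name. The coronary row is the only disease row that does not.

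**Step 3: ask whether the SAP can repair it.** Refining a code list means choosing which codes count as MI, stroke, CABG or PCI. Admitting chronic ischaemic heart disease or removing stroke would change the four-item concept, which stands in the variable name as well as in the definition. Section 9.7 says that major modifications of primary endpoint definitions are to be reflected in a protocol amendment.

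**Step 4: direction of the error.** Take three proportions of initiators:
- A: positive on the row and truly with coronary disease;
- s: positive through stroke, with no coronary disease;
- c: a coronary diagnosis but none of the four items.

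The row reports R = A + s. A row true to its label would report T = A + c. Hence R − T = s − c. The documents give neither s nor c, so the sign and the size are both unknown. Even if s and c were equal and the totals agreed, the row would contain the wrong patients.

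**Step 5: effect on the composite.** A patient in c is lost from the composite of at least one CV risk factor only if no other listed factor applies: age 65 or older, smoking, diabetes, hypertension, hyperlipidaemia (including a lipid-lowering dispensing), chronic kidney disease or stable angina. Stroke patients in s do carry a reasonable CV history item, so their entry into the composite is not an error. The composite is a partial backstop, not a complete one. For example, the drug route into the hypertension row is narrow, because Annex 8 lists only codes beginning C02, and section 9.4.1 says the Swedish patient register holds no general practice encounters.

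**The case against.** The strongest defence is that the row declares its own content in brackets, so a reader of Table 3 is not misled. The compliance outcomes in section 9.3.1 are stated for at least one CV risk factor, and there stroke belongs and most coronary patients enter by another route. Hospital events and procedures also suit these data. The Swedish register has no general practice visits, only 30% of Dutch patients in the high-budget medication dataset are also in the GP database (Table 4, note d), and section 9.9 worries about outpatient rule-out codes. Chronic coronary codes would be captured unevenly.

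Much of this stands. It limits the harm to the individual row and makes uneven capture a real cost of the broader definition. It does not rescue the row, because sections 9.7.1.2.2.1.3 and 9.7.1.3.3 report it under the short label without the bracket. Nor does uneven capture explain why stroke is counted as coronary disease.

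Three stronger readings are tempting, and the documents do not support them:
- **The row understates coronary disease.** Step 4 shows that the sign is open.
- **Old MI is excluded.** The definition asks for any MI diagnosis code, and the code list is left to the SAP.
- **A new coronary diagnosis on treatment never counts as a developed risk factor.** It can count through the stable angina row, or as hyperlipidaemia if a lipid-lowering drug is dispensed. Only a coronary diagnosis with none of the listed factors escapes.

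**Conclusion.** The point holds for the individually reported row, before initiation and on treatment. The row combines coronary events and revascularisation with stroke and leaves out chronic ischaemic heart disease and unstable angina, so it cannot be read as coronary artery disease or as stroke.

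The size and net direction of the error cannot be determined from the documents, which give no prevalences. The effect on the composite, and on the discontinuation and continuation outcomes built on it, is smaller. That rests on the assumption that many affected patients also qualify by age, hypertension, lipid-lowering drugs or stable angina.

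A reader might infer that the composite compliance outcomes are invalid, or that coronary patients rank first among those the 2021 restriction was meant for. The documents support neither. Section 7 refers to other CV risk factors without ranking them, and the composite retains most of its routes of entry. This is a definition that should be corrected because doing so is cheap and makes a reported compliance figure interpretable. It does not undermine the study's conclusions.

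**What to change.** In Table 3, split both the baseline and the on-treatment row into two:
- **Coronary artery disease:** at least one ischaemic heart disease diagnosis code (MI included), other than the stable angina codes kept in their own row, or a CABG or PCI procedure code.
- **Stroke:** at least one stroke diagnosis code.

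Keep stable angina as it is, feed both new rows into the composite of at least one CV risk factor, and list both in sections 9.7.1.2.2.1.3 and 9.7.1.3.3. The SAP code list should say whether old-MI codes count.

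At minimum, report stroke separately and rename the remainder *MI or coronary revascularisation*, so that the label matches the content.

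The cost is a change of definition wording and one more row per table. The broader definition will admit some rule-out diagnoses, which the two-code strategy already described in section 9.9 can handle. It will also capture chronic coronary codes unevenly across countries, which should be added to the limitations in that section.

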Assessment of VTE risk factors while receiving tofacitinib therapy (duration of tofacitinib therapy defined in Section 9.3.3)

VTE	Outcome: VTE risk factor	Defined as $\geq 1$ ICD-10 diagnosis code for VTE while receiving tofacitinib therapy.
Surgery, major	Outcome: VTE risk factor	Defined as $\geq 1$ procedure code for a major surgery while receiving tofacitinib therapy.
MI	Outcome: VTE risk factor	Defined as $\geq$ 1 ICD-10 diagnosis code for an MI while receiving tofacitinib therapy.
Heart failure	Outcome: VTE risk factor	Defined as $\geq$ 1 ICD-10 diagnosis code for heart failure while receiving tofacitinib therapy.
Use of combined hormonal contraceptives or hormonal replacement therapy	Outcome: VTE risk factor	Defined as ≥1 prescription dispensing of a combined hormonal contraceptives and/or hormonal replacement therapy (as identified by ATC codes) while receiving tofacitinib therapy.
Inherited coagulation disorder	Outcome: VTE risk factor	Defined as ≥1 ICD-10 diagnosis code for inherited coagulation disorder while receiving tofacitinib therapy.
Malignancy (non- metastatic and metastatic; excluding non-melanoma skin cancer)	Outcome: VTE risk factor	Defined as ≥1 ICD-10 diagnosis code for malignancy (excluding non-melanoma skin cancer) while receiving tofacitinib therapy.
Diabetes	Outcome: VTE risk factor	Defined as ≥1 ICD-10 diagnosis code for diabetes while receiving tofacitinib therapy.

Variable	Role	Operational definition
Hypertension	Outcome: VTE risk factor	Defined as ≥1 ICD-10 diagnosis code for hypertension while receiving tofacitinib therapy.
Discontinuation of tofacitinib after developing ≥1 VTE risk factors while taking tofacitinib	Outcome: VTE risk factor	Defined as ≥1 VTE risk factor while receiving tofacitinib therapy (as listed and defined above) PLUS 0 prescription dispensings for tofacitinib within a specific time window after the code for the VTE risk factor.
		Note: The time window for when to look for a tofacitinib prescription dispensing will be specific to the VTE risk factor acquired while receiving tofacitinib therapy and will be operationalized during SAP development.
		Duration of tofacitinib therapy defined in Section 9.3.3.

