Chronic kidney disease	Outcome: CV risk factor	Defined as ≥1 ICD-10 diagnosis code for chronic kidney disease while receiving tofacitinib.
Stable angina pectoris	Outcome: CV risk factor	Defined as ≥1 ICD-10 diagnosis code for stable angina pectoris while receiving tofacitinib.
Discontinuation of tofacitinib after developing ≥1 CV risk factors while taking tofacitinib	Outcome: CV risk factor	Defined as ≥1 CV risk factor while receiving tofacitinib therapy (as listed and defined above) PLUS 0 prescription dispensings for tofacitinib within a specific time window after the code for the CV risk factor.
		Note: The time window for when to look for a tofacitinib prescription dispensing will be specific to the CV risk factor acquired while receiving tofacitinib therapy and will be operationalized during SAP development.
		Duration of tofacitinib therapy defined in Section 9.3.3.
Continuation of tofacitinib after developing ≥1 CV risk factors while taking tofacitinib	Outcome: CV risk factor	Defined as $\geq 1$ CV risk factor while receiving tofacitinib therapy (as listed and defined above) PLUS $\geq 1$ prescription dispensing for tofacitinib within a specific time window after the code for the CV risk factor.
		Note: The time window for when to look for a tofacitinib prescription dispensing will be specific to the CV risk factor acquired while receiving tofacitinib therapy and will be operationalized during SAP development.
		Duration of tofacitinib therapy defined in Section 9.3.3.

 Table 3.
 Operational definitions of study variables in the selected databases

Variable	Role	Operational definition	
Analysis of malignancy ris	Analysis of malignancy risk factors in patients using tofacitinib y		
Assessment of malignancy re	Assessment of malignancy risk factors prior to initiation of tofacitinib		
Elderly at tofacitinib initiation (patients 65 years and older)	Outcome: Malignancy risk factor	Calculated as the date of tofacitinib initiation minus the patient's year of birth and reported in the following categories: $<65$ years and $\geq 65$ years.	
History of malignancy (non-metastatic and metastatic, excluding non- melanoma skin cancer)	Outcome: Malignancy risk factor	Defined as ≥1 ICD-10 diagnosis code for a malignancy (excluding non-melanoma skin cancer) in the 12 months prior to or on the day of the index tofacitinib dispensing.	

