# Table 3. Operational definitions of study variables in the selected databases

Elderly (patients 65 years	Outcome: Malignancy risk factor	Defined as patients aged 65 years or
and older)		older while receiving tofacitinib.

<sup>y In GKV claims, outpatient diagnoses are reported quarterly.

Variable	Role	Operational definition
Malignancy (non- metastatic and metastatic, excluding non-melanoma skin cancer)	Outcome: Malignancy risk factor	Defined as ≥1 ICD-10 diagnosis code for a malignancy (excluding non-melanoma skin cancer) while receiving tofacitinib.
Current smoker x	Outcome: Malignancy risk factor	Defined as $\geq 1$ ICD-10 diagnosis code for tobacco use disorder or $\geq 1$ procedure code for counselling visits for smoking or $\geq 1$ prescription dispensing (as identified by ATC code[s]) for a nicotine replacement product while receiving tofacitinib.
Discontinuation of tofacitinib after developing ≥1 malignancy risk factors while taking tofacitinib	Outcome: Malignancy risk factor	Defined as ≥1 malignancy risk factor while receiving tofacitinib therapy (as listed and defined above) PLUS 0 prescription dispensings for tofacitinib within a specific time window after the code for the malignancy risk factor. Note: The time window for when to look for a tofacitinib prescription dispensing will be specific to the malignancy risk factor acquired while receiving tofacitinib therapy and will be operationalized during SAP development. Duration of tofacitinib therapy defined in Section 9.3.3.
Continuation of tofacitinib after developing ≥1 malignancy risk factors while taking tofacitinib	Outcome: Malignancy risk factor	Defined as ≥1 malignancy risk factor while receiving tofacitinib therapy (as listed and defined above) PLUS ≥1 prescription dispensing for tofacitinib within a specific time window after the code for the malignancy risk factor. Note: The time window for when to look for a tofacitinib prescription dispensing will be specific to the malignancy risk factor acquired while receiving tofacitinib therapy and will be operationalized during SAP development. Duration of tofacitinib therapy defined in Section 0.3.2
		Section 9.3.3.

 Table 3.
 Operational definitions of study variables in the selected databases

Variable	Role	Operational definition	
Compliance to recommendations for limitations of contraindicated use z			

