### 9.7.1.2.2.1.3. Patients with CV risk factors

The proportion of patients with one or more CV risk factors, identified prior to tofacitinib initiation, will be described and tabulated overall and for each individual CV risk factor (i.e., elderly, current or past smokerx, history of diabetes, history of hypertension, history of hyperlipidaemia, history of coronary artery disease, history of chronic kidney disease, history of stable angina pectoris). Proportions will be stratified by approved indication and sex.

The proportion of patients with one or more CV risk factors, identified prior to tofacitinib initiation and no prior use of an alternative therapy (i.e., biologic), will be described and tabulated overall and for each individual CV risk factor (i.e., elderly, current or past smokerx,**Error! Bookmark not defined.** history of diabetes, history of hypertension, history

of hyperlipidaemia, history of coronary artery disease, history of chronic kidney disease, history of stable angina pectoris). Proportions will be stratified by approved indication and sex.

The proportion of patients who discontinue tofacitinib after developing one or more CV risk factors while taking tofacitinib, will be described and tabulated overall and for each individual CV risk factor (i.e., elderly, current smokerx, diabetes, hypertension, hyperlipidaemia, coronary artery disease, chronic kidney disease, stable angina pectoris). Proportions will be stratified by "RA or PsA" and "UC" and sex.

The proportion of patients who continue tofacitinib after developing one or more CV risk factors while taking tofacitinib, will be described and tabulated overall and for each individual CV risk factor (i.e., elderly, current smokerx, diabetes, hypertension, hyperlipidaemia, coronary artery disease, chronic kidney disease, stable angina pectoris). Proportions will be stratified by "RA or PsA" and "UC" and sex.

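### Risk factors counted as developed on tofacitinib need not be absent at baseline, so pre-existing chronic conditions and age ≥65 at index enter the discontinue/continue outcomes

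*Protocol*

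**What the plan says.** Section 9.7.1.2.2.1.3 of the Protocol describes the CV outcome as "The proportion of patients who discontinue tofacitinib after developing one or more CV risk factors while taking tofacitinib", with a mirror outcome for patients who continue. Sections 9.7.1.2.2.1.1 and 9.7.1.2.2.1.4 do the same for VTE and malignancy factors, and Section 9.7.1.3 repeats all of them by reporting period.

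Table 3 (Section 9.3.2) defines the on-treatment factors by their presence during treatment:
- Diabetes (VTE and CV lists): "Defined as ≥1 ICD-10 diagnosis code for diabetes while receiving tofacitinib therapy".
- Hypertension (VTE list): "Defined as ≥1 ICD-10 diagnosis code for hypertension while receiving tofacitinib therapy". The CV list also accepts an antihypertensive dispensing.
- Chronic kidney disease (CV list): at least one code for "chronic kidney disease while receiving tofacitinib".
- Malignancy (malignancy list): "Defined as ≥1 ICD-10 diagnosis code for a malignancy (excluding non-melanoma skin cancer) while receiving tofacitinib".
- Elderly (CV and malignancy lists): "Defined as patients aged 65 years or older while receiving tofacitinib".

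The CV discontinuation outcome is "Defined as ≥1 CV risk factor while receiving tofacitinib therapy (as listed and defined above) PLUS 0 prescription dispensings" in a window after the code. The notes to these outcomes call the factor acquired on treatment. What they leave to the SAP is the length of the dispensing window.

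**The concern.** The outcomes are meant to show what prescribers do when a new risk appears during treatment. The definitions do not ask whether it is new. A patient with long-standing diabetes who is coded again after index, or whose lipid-lowering drug is refilled, is counted once as starting tofacitinib with the factor and again as developing it. A patient aged 70 at index is counted as becoming elderly on treatment.

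For these patients the prescribing decision was taken at initiation, and the initiation outcomes already measure it. In the on-treatment outcomes, their continuing or stopping mostly reflects general persistence and drop-out over 12 months. If they form a large part of the denominator, the proportions say little about response to a new risk, and a real change after the 2019 or 2021 materials would be diluted in the comparison of reporting periods.

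**Working it through.** **1. The text side by side.** The outcome titles speak of developing a factor, and the notes of acquiring one. The operational rule takes any factor "while receiving tofacitinib therapy (as listed and defined above) PLUS 0 prescription dispensings for tofacitinib". The baseline and on-treatment rows for diabetes, hyperlipidaemia and chronic kidney disease differ only in timing, and no row or rule excludes patients who had the factor at baseline.

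Four further details point the same way:
- The discontinuation window starts after the code for the factor. Age has no code, so a patient already 65 or older at index has no start date.
- Sections 9.7.1.2.2.1.4 and 9.7.1.3.4 list a history of malignancy among the factors developed on treatment.
- Follow-up begins on the index date (Section 9.2.3), and the baseline factor definitions also include that day, so one index-day code can count on both sides. Quarterly dating of German outpatient diagnoses adds to this.
- Table 3 has separate outcomes for patients who turn 65 on treatment, so age is handled as a transition elsewhere, but not in the CV and malignancy factor lists.

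**2. The plan's own figure.** No figure in the protocol measures this mixing. The only relevant calculation is the precision target in Section 9.5: 0.50 × 0.50 × 1.96² / 0.10² = 96.04, rounded up to 97. It reproduces, but it concerns denominator size and not the definition.

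**3. Size for one coded factor (all inputs assumed).** Let b be baseline prevalence, r the chance of a repeat record on treatment and i the 12-month incidence among those without the factor.

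Pre-existing share = b·r / [b·r + (1 − b)·i]
- Central case, b = 0.30, r = 0.8, i = 0.05: 0.24 / (0.24 + 0.035) = 87%. Per 100 patients, 27.5 are counted as having developed the factor and 3.5 are new.
- Lowest, b = 0.10, r = 0.5, i = 0.10: 0.05 / (0.05 + 0.09) = 36%.
- Highest, b = 0.40, r = 1.0, i = 0.02: 0.40 / (0.40 + 0.012) = 97%.

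Over the grid b = 0.10, 0.20, 0.30, 0.40; r = 0.5, 0.8, 1.0; i = 0.02, 0.05, 0.10, pre-existing cases are the majority in 34 of 36 combinations. The two exceptions pair the lowest prevalence with the highest incidence.

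**4. Age alone (assumed).** Suppose 10–40% are 65 or older at index and 1–3% turn 65 in follow-up. The share already 65 or older runs from 0.10 / 0.13 = 77% to 0.40 / 0.41 = 98%.

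**5. A CV composite including age (assumed).** Let 25–35% be 65 or older at index (p), 25–50% of the rest carry a re-recorded chronic factor (c), and 5–10% of the remainder acquire one (i). Then prev = p + (1 − p)·c, new = (1 − prev)·i, and share = prev / (prev + new).
- Low corner (0.25, 0.25, 0.10): 0.4375 / (0.4375 + 0.05625) = 89%.
- High corner (0.35, 0.50, 0.05): 0.675 / (0.675 + 0.01625) = 98%.
- Below those ranges (0.15, 0.20, 0.10): 0.32 / (0.32 + 0.068) = 82%.

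**6. Effect on the result (assumed).** If a share s of the denominator is pre-existing, observed discontinuation = (1 − s)·d₁ + s·d₀, where d₁ applies to new and d₀ to pre-existing cases. With s = 0.9, d₁ = 0.50 and d₀ = 0.20, it is 0.05 + 0.18 = 0.23. A 10-point change in d₁ between reporting periods would then move the observed figure by 1 point.

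**The case against.** The strongest reply is that the intent is clear and the SAP will carry it out. The outcomes say developing, the notes say acquired, Section 9.3.2 calls the algorithms preliminary, and Section 9.9 says ascertainment intervals will be chosen with care. This does not settle the matter. The protocol states an explicit rule that contradicts the title, and the item deferred in the notes to these outcomes is the dispensing window. These are primary outcomes, and Section 9.7 sends major changes to primary endpoint definitions to a protocol amendment.

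Other points do stand and limit the concern:
- A reader might infer that all discontinue/continue outcomes consist mainly of pre-existing conditions. The documents do not support that. Acute events (MI, stroke, major surgery, CABG or PCI) are usually new when coded on treatment, and the on-treatment VTE list has no age factor.
- A reader might take the high percentages as established. They rest wholly on assumed inputs.
- The antihypertensive refill route is narrow, because Annex 8 lists only C02 codes. Refills matter more for lipid-lowering drugs.
- Results are also tabulated by individual factor, so mixing in the diabetes or elderly rows does not reach the MI or surgery rows. The overall rows remain affected.
- The response to turning 65 is measured by its own outcomes.
- Section 9.9 admits operational difficulties with VTE factors acquired after index, and for Sweden with separating prior from new VTE. It adds no exclusion and does not address chronic conditions.

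**Conclusion.** The definitions are wrong as written. They put patients with pre-existing chronic factors (for example diabetes, hypertension, hyperlipidaemia, chronic kidney disease, heart failure or malignancy) into denominators meant for newly developed ones. For the CV and malignancy lists they also add every patient already 65 or older at index, with no date from which to start the window. This follows from the text and needs no assumption.

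The size does need assumptions, because the documents give no prevalence, re-coding or incidence figures. On the ranges shown, the pre-existing share is about 36–97% for a coded factor, 77–98% for age and 89–98% for a CV composite. These figures show that the problem can be large; they do not estimate it. Acute events are much less affected. The study is descriptive, so no hypothesis test is invalidated. What fails is the meaning of the reported proportions and of their change across reporting periods.

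**What to change.** In Table 3 and Section 9.7:
- Count a factor as developed only if there is no code, procedure or dispensing for that same factor in the 12-month baseline up to and including the index day, and its first record falls after the index day. For German outpatient diagnoses, state how codes from the index quarter are allocated.
- For the CV and malignancy elderly factor, count only patients under 65 at index who reach 65 during treatment, consistent with the existing turning-65 outcomes. Start the window on the date they reach 65, or on the best approximation where only birth year is held. Table 3 calculates age at initiation from year of birth, so an exact birthday cannot be assumed.
- Replace history of malignancy in the on-treatment lists with newly recorded malignancy.
- Tabulate patients with pre-existing factors separately.

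This is a wording change that uses data already planned. The cost is smaller denominators. In the central illustration, 100 patients yield 3.5 new cases of a factor instead of 27.5 counted. With as few as 5 cases the normal-approximation half-width is 1.96 × √(0.25/5) = 0.44, far from the 0.10 in Section 9.5, so expected denominators should be stated. Some prevalent cases will remain because the look-back is only 12 months, which should be given as a limitation. Requiring the whole post-event window to be observed is a separate design choice. It would drop factors acquired late in follow-up, and it is not part of this correction.
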